### 6.2 Medical History

The medical history of the patient will be obtained. Specific information will be recorded on the eCRF relating to any prior or existing medical conditions/surgical procedures involving the following: Infectious Diseases (including viral infections, like Hepatitis B and C and human immunodeficiency virus (HIV)), Allergies, Metabolic/Endocrine/Nutritional, Hematopoietic, Musculoskeletal, Dermatologic, Head, Ears, Eyes, Nose, and Throat (HEENT), Breasts, Respiratory, Cardiovascular, Gastrointestinal/Hepatic, Genitourinary/Renal, Neurologic, and Psychiatric/Psychosocial.

In addition, specific detailed information regarding the clinical symptoms and treatment of the hemophilia will be collected. This will include the following: type of hemophilia (A or B), severity (including factor VIII or IX level), number of bleeding episodes during the past 6 months (if <6 months old, number of bleeding episodes since birth), existence of a target joint/bleeding site (i.e., a joint in which recurrent bleeding has occurred on four or more occasions during the previous 6 months or one in which 20 lifetime bleeding episodes have occurred), date of first detection of inhibitors, treatment for bleeding episodes (product and dose for each bleeding episode) in past month (or in case there were no bleeding episodes in the prior month, details from the last 2 bleeding episodes of the patient), ITI (current or in the past, including product, dose and dates of treatment).

Demographics (date of birth, race/ethnicity, sex) will also be collected.

### 6.3 Physical Examination

A standard physical examination will be performed at set timepoints during the study. All findings from this examination will be recorded on source documents and entered into the eCRF. The standard physical examination will include the following observations/measurements: Height/Weight, General Appearance, Skin, HEENT, Lymph Nodes, Heart, Lungs, Abdomen, Extremities/Joints, Neurological, and Mental Status.

The patient will be weighed every 6 weeks and dose adjustment made if necessary.

When the standard physical exam is performed and at some additional timepoints, the patient will be checked for any signs of thromboembolic events such as pulmonary embolism (e.g., shortness of breath, chest pain, cyanosis), or deep venous thrombosis (e.g., calf pain, swelling/edema, redness, venous distension, pain on dorsiflexion).

### 6.4 Vital Signs

Vital signs will be obtained at set timepoints during the study. The assessments of vital signs include systolic and diastolic blood pressures (mmHg), heart rate (beats/minute), respiratory rate (breaths/minute), and body temperature (°C or °F, sublingual or tympanic).

### 6.5 Clinical Laboratory Tests

Investigator will contact the Medical Monitor regarding any patient who weighs <12 kg for adaptation of the blood sample schedule to the patient's body weight in consideration of ICH Harmonised Tripartite Guideline "Clinical Investigations of Medicinal Products in the Paediatric Population, ICH Topic E 11," ([http://www.ema.europa.eu/docs/en\\_GB/document\\_library/Scientific\\_guideline/2009/09/WC500002926.pdf](http://www.ema.europa.eu/docs/en_GB/document_library/Scientific_guideline/2009/09/WC500002926.pdf)). Blood volume drawn cannot exceed 3% of the total blood volume of the patient during a period of 4 weeks and cannot exceed 1% of the total blood volume at any single time.

For subjects < 12 kg, the minimum weight requirement is 10.5 kg, when blood will be collected by peripheral venipuncture. The investigator must contact the Medical Monitor to discuss enrollment of any subject weighing < 12 kg with an indwelling catheter, Port-a-cath or PICC line. The following total amounts of blood will be taken at each visit as described in Table 2.

**Table 2. Total Amounts of Blood Taken During the Study**

Visit	Child weighs <12 kg at screening	Child weighs ≥12 kg to <19 kg at screening	Child weighs ≥19 kg at screening
Screening	7.5 mL	9.6 mL	15.2 mL
Visit 1	7.8 mL	9.6 mL	15.1 mL

Visit	Child weighs <12 kg at screening	Child weighs ≥12 kg to<19 kg at screening	Child weighs ≥19 kg at screening
Week 3	2.5 mL	2.5 mL	3 mL
Week 6	2.5 mL	2.5 mL	3 mL
Week 12	6.5 mL	7 mL	10 mL
Week 18	2.5 mL	2.5 mL	3 mL
Week 24	8 mL	9.7 mL	14 mL
Every 6 weeks after Week 24	2.5 mL	2.5 mL	3 mL
End of Study/Early Termination	8 mL	9.2 mL	15 mL

## 6.5.1 Laboratory Parameters

### 6.5.1.1 Safety Laboratory Tests

Clinical safety laboratory tests will include the following and will be carried out by the central laboratory for the study as presented in Table 3:

**Table 3. List of Laboratory Tests**

Hematology:	Serum Chemistry:

 
- Hematocrit (Hct)
 
- Hemoglobin (Hgb)
 
- Platelet count
 
- White blood cell (WBC) count with differential (automated)
 
- CD4 count
 
	
 
- Albumin (ALB)
 
- Alkaline phosphatase (ALK-P)
 
- Alanine aminotransferase (ALT; SGPT)
 
- Aspartate aminotransferase (AST; SGOT)
 
- Creatinine
 
- Gamma-glutamyl transferase (GGT)
 
- Lactate dehydrogenase (LDH)
 
- Total protein
 

Coagulation	

 
- FVIII or FIX
 
- FVIII or FIX inhibitors
 
	

 Only at Screening

 In hemophilia A patients only

 In hemophilia B patients only

#### 6.5.1.2 Coagulation Tests

Factor VIII (in hemophilia A patients) and factor IX (in hemophilia B patients) concentration will be assessed at Screening. The titer of inhibitors to factor VIII (in hemophilia A patients) or factor IX (in hemophilia B patients) will be assessed at Screening, 24 weeks, and EOT at the central laboratory. The Bethesda assay will be used for inhibitor testing.

#### 6.5.1.3 Drug Concentration Tests

FVIIa concentration will be determined in all patients who have PK assessments done after receiving study drug in Phase A. The concentration will be determined by using a validated modified activity assay (Staclot® VIIa-rTF from Diagnostica Stago) in a single central laboratory.

#### 6.5.1.4 Immunogenicity Testing

Serum samples to test for antibodies against LR769 and any host related impurities will be taken at set timepoints during the study. Testing for antibodies against LR769 will be done by a screening assay (electrochemiluminescent method) that is able to detect all antibody isotypes. If the sample is screen positive (which is expected in about 5% of samples), the sample will be tested in a confirmatory assay using binding inhibition as a way to confirm the specificity of the signal seen in the screening assay. If confirmed positive, the sample will be tested in an assay that has been set up to determine if antibodies in patient plasma that are known to bind LR769 (as suggested by the screening and confirmatory assay) will also *neutralize* FVIIa clotting activity. A dot blot assay has been developed to screen the patient samples for reactivity to rabbit's milk proteins. This will allow identifying patients that are generating an immune response to milk proteins as a result of study drug treatment.

#### 6.5.1.5 Sample Storage

Serum samples (if available) will be stored (for a maximum of 5 years after the end of the study) for purposes of any safety evaluations deemed necessary in the future (e.g., infectious disease evaluations). These samples will be stored by the Sponsor (or designee) in a central location.

#### 6.5.2 Sample Collection, Storage, and Shipping

A separate laboratory manual will be prepared that describes the appropriate sample collection, storage, and shipping procedures.

### 6.6 Dispensing Study Drug

When treatment is taking place in the hospital or hemophilia treatment center in Phase A, or for severe bleeding episodes in Phase B, drug will be prepared by and dispensed to the study staff according to the local study center's procedures. After the patient completes Phase A without any safety concerns, the patient/parent, after due training by the study staff, will receive study medication as well as materials for reconstitution and administration (e.g.,

alcohol swabs, syringes, butterfly needles, etc.) to store at home, in order to be able to treat subsequent mild/moderate bleeding episodes at home.

## 6.7 Pharmacokinetic Assessments

In Phase A, blood draws will occur at baseline (prior to LR769 administration) in all patients. To reduce the amount of blood draws, subsequent sampling will be done in approximately half of the patients (sampling schedule 1) at  $10\pm 2$  minutes, 1 and 4 hours ( $\pm 10$  minutes), and the other half of the patients (sampling schedule 2) at  $30\pm 5$  minutes and 2 and 8 hours ( $\pm 10$  minutes) relative to the start of infusion of study drug. FVIIa concentrations will be determined using a validated modified activity assay (Staclot® VIIa-rTF, Diagnostica Stago) at Good Biomarker Sciences (Leiden, The Netherlands).

## 6.8 Efficacy Assessments

Efficacy of the treatment of each bleeding episode will be assessed by the parent(s)/guardian or other caregiver in conjunction with the patient where possible (e.g., depending on age) and noted in the patient diary. In case of treatment the efficacy assessment in the hospital is *also* done by the physician and recorded in the patient's records. Response to treatment will be rated as "none," "moderate," "good," or "excellent,"

These are defined as follows:

- None: no noticeable effect of the treatment on the bleeding or worsening of patient's condition. Continuation of treatment with the study drug is needed.
- Moderate (fair): some effect of the treatment on the bleeding is noticed, e.g., pain decrease or bleeding signs improvement, but bleeding continues and requires continued treatment with the study drug.
- Good: symptoms of bleeding (e.g., swelling, tenderness, and decreased range of motion in the case of musculoskeletal hemorrhage) have largely been reduced by the treatment, but have not completely disappeared. Symptoms have improved enough to not require more infusions of the study drug.
- Excellent: full relief of pain and cessation of objective signs of bleeding (e.g., swelling, tenderness, and decreased range of motion in the case of musculoskeletal hemorrhage). No additional infusion of study drug is required.

Source: (Amby et al., 2009)

A response of none or moderate is usually followed by continued treatment with the study drug; a response of good or excellent means that no further treatment is needed or, in the case of a severe bleeding episode, the dosing interval can be increased. This four point scale is a frequently used tool in hemophilia to assess efficacy of treatment (Amby et al., 2009). If a bleeding episode is treated in the hospital, the physician will be asked to assess efficacy using the same scoring system at the same timepoints.

Additionally, as part of the patient diary, a VAS to rate pain will be completed by the parent/guardian/ caregiver in conjunction with the patient where possible (e.g., depending on age) to assess the response of pain to treatment.

Efficacy assessment of LR769 to treat a mild/moderate bleeding episode will occur within 15 minutes prior to each administration of study drug.

- Mandatory efficacy assessment timepoints for 75 µg/kg – 3, 12, and 24 hours after initial dose.
- Mandatory efficacy assessment timpoints for 225 µg/kg – 9, 12, and 24 hours after initial dose.

If additional adminstrations are needed after the initial injection then assessemnts are to be completed within 15 minutes prior to each subsequent injection.

Efficacy assessment of LR769 to treat severe bleeding episodes will be assessed within 15 minutes prior to each administration of study drug.

- Mandatory efficacy assessment timepoints for 75 µg/kg – 2, 12, and 24 hours after initial dose.
- Mandatory efficacy assessment timpoints for 225 µg/kg – 6, 12, and 24 hours after initial dose.

If additional adminstrations are needed after the initial injection then assessemnts are to be completed within 15 minutes prior to each subsequent injection.

The timepoint for the primary evaluation of efficacy will be 12 hours after first administration of study drug.

Patient diaries will be used for the collection of information on the efficacy of treatment, as assessed by the parent/guardian/caregiver in conjunction with the patient where possible (e.g., depending on age). Efficacy of treatment assessed by the physician during severe bleeding treatment in clinic will be documented in patient's source records.

In addition to the above score the following information will be collected for each bleeding episode (by patient for mild/moderate bleeding episodes and by physician for severe bleeding episodes treated onsite):

- Date and start time (first symptoms) of bleeding episode
- Cause of bleeding episode
- Severity of bleeding episode (according to Table 1)
- Type and anatomical site of bleeding episode
- In case of joint: target joint or not; specify joint

- Did any recurrence of bleeding episode (defined as bleeding in the same joint/anatomical location within 24 hours after an initial “good” or “excellent” response) occur
- Did the bleeding episode require any alternative treatment (including information on the nature of the alternative treatment, start date/time and stop date/time of alternative treatment, if applicable)
- Did the bleeding episode require visit to the hospital
- Occurrence of pain (prior to the 1st infusion of study drug to treat this bleeding episode) and progression/resolution of pain assessed at each efficacy assessment timepoint. Pain caused by a bleeding episode will be measured on a VAS in millimeters from 0 (no pain) to 100 (worst possible pain).
- Time to cessation of bleeding episode
- Date, dose and total volume, time of administration of each dose, lot numbers, and number of vials used.

All assessments described as done by the patient may be done by the parent/legal guardian or other caregiver depending on the age of the patient.

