### 7.2.1.3 3, 6, 9, 12, 15, 18, 21 hours after first administration

- AE assessment (assessed over a period of 21 hours after first study drug administration, reported by the patient/parent in the patient diary if home treatment and in addition by study staff if in hospital or hemophilia treatment center)
- Efficacy assessments (within 15 minutes before each new administration of the study drug) to be done by the patient/parent if home treatment and by study staff if in hospital or hemophilia treatment center in addition to patient assessments
- Record date, time and outcome of the assessments in patient diary (patient/parent); if in hospital or hemophilia treatment center in patient records by study staff in addition to patient's assessment
- Assessment of concomitant medication

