### **ADMINISTRATION OF STUDY DRUG:**

#### When in 75 $\mu$ g/kg dose treatment regimen:

- If response to treatment 3 hours after last administration is unsatisfactory (i.e., efficacy assessment is not rated as good or excellent): a  $\leq$  2 min IV push of 75

$\mu\text{g}/\text{kg}$  of LR769 may be administered. This may be repeated, if needed every 3 hours up to and including 21 hours after first administration.

- If response to treatment 3 hours after the first or any of the subsequent administrations is satisfactory (i.e., efficacy assessment is rated as good or excellent): no study drug administration. Perform the 3 hourly efficacy assessments until 3 hours after the last administration as well as the 12 hours efficacy assessments (if not already done).

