#### When in 225 $\mu\text{g}/\text{kg}$ dose treatment regimen:

- If response to treatment 9 hours after first administration is unsatisfactory (i.e., efficacy assessment is not rated as good or excellent): a  $\leq 2$  min IV push of 75  $\mu\text{g}/\text{kg}$  of LR769 may be administered. This may be repeated, if needed every 3 hours up to and including 21 hours after first administration.
- If response to treatment 9 hours after first administration, or 3 hours after any subsequent administrations, is satisfactory (i.e., efficacy assessment is rated as good or excellent): no study drug administration. Perform the 12 hours efficacy assessments (if not already done).
- Record date, time and total dose of study drug as well as number and lot of vials used for preparation in patient diary (by the patient/parent); if in hospital or hemophilia treatment center in patient records by study staff.
- If, because of an initial sufficient response at 9 hours post initial dose of study drug, no additional study drug is administered, it may re-started before the 24-hour cut off in case of a recurrence of a bleeding episode. This should be noted in the patient's diary.

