#### **ADMINISTRATION OF STUDY DRUG:**

##### When in 75 $\mu$ g/kg dose treatment regimen:

- If response to treatment 2 hours after first or any subsequent administration is unsatisfactory (i.e., efficacy assessment is not rated as good or excellent): a  $\leq$  2 min IV push of 75  $\mu$ g/kg of LR769 may be administered.
- If 2 hours after last administration the bleeding episode has improved (i.e., efficacy assessment is rated at least as moderate): change to treatment at 3-hour intervals for 1-2 days until good or excellent result is reached
- After 1-2 days, the interval may be increased to 4-12 hours depending on the type of bleeding episode for as long as needed

When in 225 µg/kg dose treatment regimen:

- If response to treatment 6 hours after first administration is unsatisfactory (i.e., efficacy assessment is not rated as good or excellent): a  $\leq 2$  min IV push of 75 µg/kg of LR769 may be administered. This will be repeated every 2 hours until improvement in bleeding symptoms is observed
- If response to treatment after the first or any subsequent administration is satisfactory (i.e., efficacy assessment is rated as good or excellent): change to 3 hour intervals of treatment for 1-2 days
- After 1-2 days, the interval may be increased to 4-12 hours depending on the type of bleeding episode for as long as needed
- Record date, time and total dose of study drug as well as number and lot of vials used for preparation in patient diary (by the patient/parent); if in hospital or hemophilia treatment center in patient records by study staff.

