### 9.2 Determination of Sample Size

The proportion ( $\hat{p}$ ) of mild/moderate bleeding episodes treated with each dose of LR769 that are classified as being successfully treated will be compared with an objective performance criterion (OPC) of 0.55. A one-sided, one-sample normal approximation test, with an alpha = 0.0125 (adjusted from 0.025 to 0.0125 to account for multiplicity of testing), will be used to test the null hypothesis that  $p \leq 0.55$  versus the alternative hypothesis that  $p > 0.55$ , where  $p$  is the true proportion of mild/moderate bleeding episodes that are classified as successes. (Note: The standard error used in the denominator of the test statistic will account for the correlation among bleeding episodes for a given patient.) This will be done for each treatment regimen.

With the assumptions of a true proportion of success of 0.70, a correlation among bleeding episodes for a given patient of 0.1, and an OPC of 0.55, a sample size of 22 patients with a total of 352 mild/moderate bleeding episodes (assuming 8 bleeding episodes per treatment regimen per patient) will provide statistical power  $\geq 80\%$ . The study will enroll at least 24 patients, in order to account for dropouts and potential unevaluable bleeding episodes.

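### The first required response rating is at 3 h on 75 µg/kg but 9 h on 225 µg/kg (2 h and 6 h for severe bleeds), and nothing in the supplied text allows for this in the by-regimen time-to-response results

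*Protocol*

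**What the plan says.** **Mild/moderate bleeds.** Protocol Section 6.8, repeated in the synopsis, gives two lists: "Mandatory efficacy assessment timepoints for 75 µg/kg – 3, 12, and 24 hours after initial dose" and "Mandatory efficacy assessment timpoints for 225 µg/kg – 9, 12, and 24 hours after initial dose". Further ratings fall just before each later injection.

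**Severe bleeds.** The first required rating is at 2 h on 75 µg/kg. On the other regimen it is later: "Mandatory efficacy assessment timpoints for 225 µg/kg – 6, 12, and 24 hours after initial dose". Footnote 5 of the severe table in Appendix 1 expressly removes the 2 h and 4 h ratings on 225 µg/kg.

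**Other text on mild/moderate ratings.**
- The heading of Section 7.2.1.3 lists "3, 6, 9, 12, 15, 18, 21 hours after first administration" without splitting by regimen.
- Under that heading, the 75 µg/kg instructions say "Perform the 3 hourly efficacy assessments until 3 hours after the last administration". The 225 µg/kg instructions begin "If response to treatment 9 hours after first administration is unsatisfactory" and mention no earlier rating.
- The mild/moderate table in Appendix 1 marks an efficacy rating at 3 h and 6 h. Its footnote 3 exempts 225 µg/kg from dosing at those times and sits on the drug row only. Footnote 4 ties ratings to planned doses and to 3 h after the last dose. Footnote 5 makes only 12 h and 24 h unconditional.

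**Analysis.** Section 9.6 names time to a good or excellent assessment as a secondary endpoint, estimated by Kaplan-Meier for each regimen with right-censoring. SAP addendum Section 2 adds time plots by dose. Table Addendum 14.2.8.1.1 puts mean, median and Kaplan-Meier quartiles in adjacent regimen columns and labels the quantity as time required to reach a response. For the Kaplan-Meier method the addendum refers to the main SAP.

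**The concern.** A response can be recorded only when someone rates the bleed. If one regimen is first rated at 3 h and the other at 9 h, a bleed that resolves at 2 h is recorded as a 3 h response in one column and a 9 h response in the other. Ordinary Kaplan-Meier treats both as exact event times, so the schedule alone can make 75 µg/kg look faster early on.

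The protocol's name for the endpoint, time to assessment, at least hints at this. The addendum's label does not, and a reader of the shell table would compare the columns as speed of effect. At stake are a named secondary endpoint and the addendum's by-regimen summaries and rating-based plots. The addendum's plot of bleeds still ongoing uses end-of-bleed time and is not touched.

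**Working it through.** The plan gives no figure for time to response, so there is none to reproduce. Its one design figure, power of at least 80% for the 12 h test, is separate. With design effect 1 + 7 × 0.1 = 1.7, effective n is 176/1.7 = 103.5 per regimen. At one-sided 0.0125, power is 81.5% (null variance at the critical value) to 86.2% (alternative variance throughout).

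**Assumptions.** True response times are the same in both regimens: F(t) = 1 − exp(−(t/s)^k), with s set so that F(12) = p. The base case is k = 1, p = 0.70. Section 9.2 states "With the assumptions of a true proportion of success of 0.70" for composite success at 12 h; it is borrowed here for a first good/excellent rating. Each true time moves up to the next rating. Quartiles are the first rating time at which F reaches 0.25, 0.50 or 0.75. Means are over responders by 24 h. Bleeds not yet responding on 75 µg/kg are taken to be rated 3-hourly.

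**Mild/moderate grids for 225 µg/kg.**
- (a) 9, 12, …, 24 h: the Section 6.8 list and the 225 µg/kg instructions.
- (b) 3, 9, 12, …, 24 h: footnote 4 read literally (3 h after the single dose, then before the planned 9 h dose).
- (c) 3, 6, 9, …, 24 h: the table columns and the 7.2.1.3 heading.

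**Base case.** F(t) = 1 − 0.3^(t/12), so F(3) = 0.260, F(6) = 0.452, F(9) = 0.595, F(24) = 0.910.

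| Grid | Q1 | Median | Mean |
|---|---|---|---|
| 75 µg/kg | 3 h | 9 h | 9.2 h |
| 225 (a) | 9 h | 9 h | 11.5 h |
| 225 (b) | 3 h | 9 h | 9.8 h |
| 225 (c) | 3 h | 9 h | 9.2 h |

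Mean gap under (a): responders by 3 h move by 6 h and those from 3 to 6 h by 3 h, so (6 × 0.260 + 3 × 0.192)/0.910 = 2.3 h. Under (b) only the second group moves: 3 × 0.192/0.910 = 0.6 h.

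**Other inputs, mild/moderate.**
- Exponential, p from 0.55 to 0.90: mean gap 1.9 to 3.4 h under (a), 0.6 to 0.8 h under (b).
- Medians separate (6 versus 9 h) under (a) and (b) once F(6) reaches 0.50, that is from p = 1 − 0.5² = 0.75. With k = 0.7 they already separate at 0.70.
- k = 0.7 at p = 0.70: means 7.9 h (75), 11.0 h (a), 8.5 h (b). With k = 1.5: 10.4, 11.9 and 11.1 h.
- Slow case, k = 1.5 and p = 0.55: Q1 is 9 h on every grid; means 12.0, 13.2 and 12.5 h.
- Reversal under (a): if 225 µg/kg were truly twice as fast (true medians 3 h versus 6 h), the recorded medians would be 9 h for 225 µg/kg and 6 h for 75 µg/kg.

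**Severe bleeds.** Ratings follow doses. Section 7.2.2.3 starts 2-hourly on 75 µg/kg and, after improvement, says "change to treatment at 3-hour intervals for 1-2 days until good or excellent result is reached". Two grid pairs were therefore tried.
- 2-hourly (2, 4, … versus 6, 8, … h), base case: Q1 4 versus 6 h, median 8 h in both, mean 8.6 versus 9.8 h.
- 3-hourly after the first rating, with 12 h and 24 h always rated (2, 5, 8, 11, 12, 14, … versus 6, 9, 12, … h), base case: Q1 5 versus 6 h, median 8 versus 9 h, mean 9.0 versus 10.0 h.

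Over k = 0.7 to 1.5 and p = 0.55 to 0.90, the mean is later on 225 µg/kg by about 0.4 to 2.3 h. On the 3-hourly pair the median contrast changes sign (75 versus 225): 8 versus 9 h in the base case, 8 versus 6 h at k = 1 and p = 0.80, and 11 versus 9 h at k = 1.5 and p = 0.70.

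**The case against.** The best defence has three parts.

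1. **The mild/moderate gap may not exist.** The required times can be read as a minimum. The Appendix 1 table marks 3 h and 6 h for everyone, and the severe footnote shows that the drafters named efficacy ratings when they meant to remove them. On that reading the gap is nil. This stands in part: footnote 4 and the 225 µg/kg instructions point the other way, so the text is ambiguous. A reader might infer that the mild/moderate estimates are certainly biased. The documents do not support that; bias depends on which schedule sites followed.

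2. **The main SAP may deal with it.** The addendum defers to main SAP v2.0, which is not supplied. So the documents cannot show that the sponsor overlooked the problem, only that the supplied text contains no allowance. The protocol passages still need reconciling whatever that SAP says.

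3. **The consequence is modest.** The endpoint is named time to assessment, no between-regimen test of it is stated, and Section 9.5.1 expects severe bleeds to be a minority, analysed descriptively. All of this is true and limits the weight of the point. It does not remove the problem of adjacent columns headed as time to reach a response.

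**Conclusion.** The point holds as a limited one that should be corrected. Required first ratings differ by regimen: 3 h versus 9 h for mild/moderate bleeds and 2 h versus 6 h for severe bleeds. The severe difference is explicit; the mild/moderate one depends on the reading. With no true difference, the recorded mild/moderate mean gap in the base case is 2.3 h, 0.6 h or nil on readings (a), (b) and (c). Q1 differs by 6 h on (a) only. These sizes rest on an assumed response curve and a borrowed 0.70.

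Two stronger readings should be resisted. The 12 h primary analysis is not affected, because a 12 h rating is required in both regimens. No fixed median gap can be claimed for severe bleeds, because its sign depends on how the grids line up; only the later mean on 225 µg/kg is consistent over the range tried.

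**What to change.** 1. Reconcile Sections 6.8 and 7.2.1.3 with the mild/moderate Schedule of Events on which ratings apply on 225 µg/kg.
2. The addendum analyses run after database lock, so tabulate by regimen how many bleeds were actually rated before 9 h (before 6 h for severe bleeds). This shows which reading sites followed.
3. Unless the main SAP already does so, analyse time to response as interval-censored, between the last non-response rating (or first dose) and the first response rating.
4. Otherwise, do not set Q1, median or mean time to response side by side by regimen. Limit by-regimen cumulative comparison to rating times common to both: 9 h onward for mild/moderate bleeds, and 12 h and 24 h for severe bleeds unless the actual ratings show a shared grid. Footnote the different grids.

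The cost is document reconciliation, some SAP wording and a little more analysis. Ratings that were not collected cannot be recovered. Under the Section 6.8 grid a nonparametric interval-censored estimate gives no detail between 0 and 9 h on 225 µg/kg. A parametric fit does recover the early quartiles: an exponential model fitted to 100,000 simulated exponential times gave Q1 2.86 h and median 6.88 h on grids 75, (a) and (b), against true values of 2.87 h and 6.91 h. That relies on the model being right.
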